## **6.0 Procedures Involved\***

### **Design Overview**

Preparation. During the first 6 months of the study, my team will work closely with key stakeholders (i.e., clinic director, practice manager, and nurse practitioner) in the FSU SeniorHealth™ clinic to coordinate initial contact with patients about the study. Initial contact will include posting flyers in the SeniorHealth clinic, handing out flyers during appointments, and emailing flyers or calling patients who have consented to be contacted about FSU research studies (a consent process, which is completed as part of the normal SeniorHealth intake packet), posting flyers in the Westminster Oaks monthly newsletter, and patients will be able to fill out a contact card with their name, phone number, and email that will be placed in a locked “drop box” in the SeniorHealth clinic. A study team member will collect these cards weekly to enter into a secure screening waitlist. Patients may also discuss interest with their provider or contact the study team directly using the information on the study flyer. If we are unable to recruit the full sample through FSU SeniorHealth, we will expand recruitment to community older adults more broadly, including individuals from the Institute for Successful Longevity participant registry. Community participants will be recruited through flyers, e-mails, and phone calls. Potential participants will only be contacted through e-mail or phone calls if they have previously provided consent to be

contacted for research purposes. Potential participants will be added to a secure screening waitlist, which will include only their name and phone number. This screening waitlist containing potential participant contact information will be stored in a password protected document. Contact information for potential participants will be destroyed for any participant who does not qualify and consent to remain in the study.

Screening phone call. After confirming interest in being contacted about the study, participants will be contacted by a member of the research team and screened for eligibility. This screening will include a telephone MoCA, sections 1 and 4 from the Functional Status Questionnaire, a brief memory complaint scale, a brief self-rated pain during the past week (0-10), and self-reported height, weight, and age. Participants will also be asked to report any restrictive dietary or medical conditions that may make them unable to change their nutrition. Participants will be compensated with a \$5 e-gift card for completing the screening and will be asked to provide their full name and email address to receive the gift card. This contact information will not be retained for future research purposes unless participants consent to be contacted for future studies. All screened participants will be provided with a handout on healthy living designed in collaboration with the SeniorHealth physicians. If participants are eligible, then they will be sent an online consent form via REDCap, which they will read and review using HIPPA-compliant Zoom with a member of the research team before signing. The study team will then complete a final eligibility check of the patient's EHR, self-reported health conditions, or provided health records and review with a SeniorHealth physician to confirm eligibility and ensure participant's safety. The SeniorHealth physician will be blinded to participant identify of non-clinic participants. Participants who are eligible and consent to participate will have screening data linked with other study data, in order to reduce redundancy in assessment measures.

Pre-intervention EHR data download & collection of Health Records(Time 0). FSU SeniorHealth patients will be asked to provide our team access to relevant EHR data. Participants who are not patients at FSU SeniorHealth will be asked to provide the same records if possible, but self-reported health conditions and medications will be accepted. Our team will extract and clean relevant EHR/health data on participants who consent to participate in the study. Data from EHR/health records will be used to conduct a secondary eligibility screening to determine if there are any other major health conditions that will exclude participants from the study. Data requested will only include the minimum PHI necessary to complete the proposed study. Data from the EHR or requested health records will include the following information only from appointments pertinent to the study: patients' problem/diagnostic list, medication list, patient vitals, metabolic panels, HbA1C, potassium, CRP, scores on recent cognitive and psychological assessments (i.e., MoCA, depression inventories), and relevant provider notes about a patient's cognitive functioning and pain. Data from the EHR/health records will be used to calculate a CAIDE dementia risk score (Exalto et al., 2014), which includes age, education, sex, cholesterol, BMI, and systolic blood pressure (See Figure 1). The FSU SeniorHealth EHR is maintained on Athena and thus all the information will be accessed from Athena by the study PI, who is a licensed clinician who has completed the required HIPAA and Privacy trainings required to access this information. These data will include the participants MoCA scores, GDS, and FSQ scores or relevant qualitative data about their activities of daily living, and demographic characteristics. We will also include laboratory results that may be relevant to cognitive outcomes for secondary data analyses, including: HbA1c, glucose, potassium,

blood pressure, and cholesterol. Laboratory data that is pulled from the EHR, will be used as a comparison to metabolic and HbA1c data obtained from a blood draw during two in-person assessments.

Baseline Assessment (Time 1). In addition to embedded EHR and other health record data, we are collecting additional data to evaluate the personal impacts of the intervention. This in-person assessment will include: the Repeatable Battery of Neuropsychological Status (RBANS update – form A), GAS, PHQ-9, FSQ, ISEL, MSQ, CAIDE risk score, OPQOL, GSE, PSQI, SCOFF, social support, self-efficacy, a verbal pain descriptor scale, the Brief Pain Inventory, The WOMAC-Pain scale, the PANAS, PSS, the WHY-MPI, and the Roland-Morris Pain and Pain-related Disability scale, a fasting blood draw for a comprehensive metabolic panel and HbA1C (completed by a certified medical assistant), a weight and body composition assessment, and basic vitals (blood pressure and heart rate). Participants will be scheduled in the morning for these assessments in order to allow approximately 10-hour fasting for the blood draw. This assessment will be completed in-person following COVID-19 precautions (described in section 14), and patient participants will be compensated \$30 for their time.

Post-intervention Assessment (Time 2). Participants will complete this assessment in the final weeks of the program, in order to assess participants when they are in ketosis. Participants will be asked to return their ketone logs either electronically, reported over the phone, or via mail to the study PI. The research team will complete qualitative interviews with participants to collect information about barriers and facilitators to completing the program and adhering to KN. Participants will complete the RBANS update – Form B, the PHQ-9, FSQ, MSQ, GAS, CAIDE risk score, OPQOL, PSS, PSQI, social support (ISEL), self-efficacy (GSE), group cohesion, a verbal pain descriptor scale, the Brief Pain Inventory, The WOMAC-Pain scale, the PANAS, the Roland-Morris Pain and Pain-related Disability scale, the WHY-MPI, and participants' global impression of change, a second fasting blood draw for comprehensive panels (completed by a certified medical assistant), a weight and body composition assessment, and basic vitals (blood pressure and heart rate). Participants will be scheduled in the morning for these assessments in order to allow approximately 10-hour fasting for the blood draw. This assessment will be completed in-person following COVID-19 precautions, and patient participants will be compensated \$30 for their time.

Post-intervention Assessment (Time 3). Patient participants will complete this assessment approximately 3 months after completing the intervention program, in order to assess long-term maintenance. The research team will complete qualitative interviews with participants to collect information about barriers and facilitators to adhering to KN long-term. Participants will complete the RBANS Update – form C, the PHQ-9, FSQ, MSQ, GAS, CAIDE Risk score, OPQOL, PSQI, social support (ISEL), self-efficacy (GSE), a verbal pain descriptor scale, the Brief Pain Inventory, The WOMAC-Pain scale, the PANAS, PSS, the WHY-MPI, the Roland-Morris Pain and Pain-related Disability scale, the Client Satisfaction Questionnaire (8-item), and participants' global impression of change in pain. This assessment will be completed in-person following COVID-19 precautions and patient participants will be compensated \$30 for their time.

Participants who express barriers to completing the 3-month post-intervention assessment in person will have the option to complete this assessment remotely if they

choose to. In the even that a participant chooses to complete the Time 3 assessment remotely, the following procedures will be conducted: a research assistant will schedule a phone call with the participant at a time that is convenient to them to complete the qualitative interviews with participants and collect self-reported height, weight, and ketone test (if available); participants will be asked to complete questionnaires via REDCap by following a link to the survey that will be emailed to them by a team member; lastly, due to the nature of the RBANS, participants who choose to complete the Time 3 assessment remotely will not be asked to complete the RBANS Update – form C. Participants will receive the same amount of compensation, \$30, for their time upon completing the assessment procedures.

Post-intervention EHR data download and Provider Assessment (Time 4). Approximately six months post-intervention, we will complete a final data extraction from the EHR for SeniorHealth patients, which will include the same data as Time 0. We will also request updated health records from non-FSU SeniorHealth clinic participants. Additionally, we will complete semi-structured interviews with the clinic providers to assess implementation barriers and facilitators. Providers will also complete quantitative measures on implementation acceptability (i.e., Modified version of the Assessment of Fit Scale for outpatient clinics). Provider participants will be compensated with a \$25 gift card for their time.

Weekly Assessments. Throughout the active intervention phase, participants will also complete a weekly online survey to assess information about their weight, health symptoms (MSQ), mood (PHQ-9), anxiety (GAS), stress (perceived stress scale), daily ketone levels, response to adherence and barriers to KN, pain, group cohesion, and social support. Participants will be asked to mail or email their food diaries to the study team each week to assist in monitoring nutritional adherence and safety.

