## 2.0 Objectives\*

- **Objective 1:**

Assess feasibility and acceptability of all protocol components of a pilot pragmatic trial testing a 6-week telehealth KNA program compared to a KN information only group for older adults with possible or pre-MCI in the community and at a senior health clinic to prepare for a full-scale trial.

Specifically, we will examine the feasibility of the recruitment, retention, assessment, electronic health record (EHR) downloads, and intervention delivery methods through the FSU SeniorHealth™ clinic. If we determine it is not feasible to recruit the full sample through this clinic, we will expand recruitment to the community.

We hypothesize that

- *The study protocol (MI-CBT KNA program) will result in high patient retention (90%) and patient attendance of intervention sessions (80%), and*
- *A centralized MI-CBT telehealth delivery approach will be associated with high intervention acceptability ratings from patients and key stakeholders.*
- *MI-CBT KNA program will result in higher adherence to KN compared to the KN information-only group as evidenced by higher levels of ketones at week 6 of the intervention using at-home ketone urinalysis test strips.*

To test these hypotheses, we will use a mixed methods approach using qualitative interviews, quantitative measures of patient satisfaction with the intervention (using the Client Satisfaction Questionnaire) and provider perception of the overall fit of the intervention in the clinic, and of patient intervention attendance and study attrition. Qualitative data from providers and patients will be thematically coded to further examine acceptability and barriers to implementation.

- **Objective 2:**

Assess signal of initial effect of the KNA program on important clinical outcomes and adherence relative to a KN information-only condition.

We hypothesize that *patients in the KNA condition, relative to the KN-only condition, will show 1) higher rates of clinically significant improvements on the RBANS total scale scores, improvements in daily functioning (FSQ), decreases in patient CAIDE risk score, improvements in HbA1C levels and comprehensive metabolic panels, and improvements in self-reported pain using the Rolland-Morris Pain scale, and 2) improved adherence to KN, as evidenced by higher levels of measurable urine ketones in the KNA condition compared to the KN-only condition.*

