#### **4.0 Study Endpoints\***

This study will focus on assessing the feasibility and acceptability of all protocol components of a pilot pragmatic trial, testing a 6-week telehealth KNA program compared to a KN information only group for older adults with possible MCI in the community and at a senior health clinic to prepare for a full-scale trial. We will use a mixed methods approach using qualitative interviews, quantitative measures of provider's perception of the overall fit of the intervention in the clinic, and of patient intervention attendance and study attrition. Qualitative data from providers and patients will be thematically coded to further examine acceptability and barriers to implementation.

We will also focus on assessing signal of initial effect of the KNA program on important clinical outcomes and adherence relative to a KN information-only condition. Data on clinical outcomes will be extracted or requested from patient health records before and after engaging in the intervention and to compare group differences. Patient participants will also complete assessments in-person, following appropriate COVID-19 precautions, pre- and post-intervention.

We expect that patients in the KNA condition will have higher rates of transferring to the normal range on the RBANS, greater improvements in functional status on the FSQ, and greater improvements in self-reported pain and other health indices. Additionally, we expect higher rates of measurable ketones (trace or higher) in the KNA program compared to KN-only based on daily, at-home urinalysis test strips. Combined, these data will provide important information about the clinical effects of the programs and feasibility of the proposed study components for a larger PCT.

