## 9.0 Inclusion and Exclusion Criteria\*

### Study Population

Older adults, between the ages of 60-85, and with possible or pre-mild cognitive impairment (MCI) were chosen in order to specifically assess the effect of the intervention on individuals at higher risk for converting to AD. These individuals may observe the greatest cognitive benefits from the intervention, while not requiring a caregiver or significant other to provide assistance or consent. The ages 60-85 were chosen, as this age range is often where early signs of dementia begin to emerge on neuropsychological testing.

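### Patient satisfaction, a quantitative measure for Objective 1, is collected only about 3 months after the programme ends; also give it at Time 2 and at withdrawal

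*Protocol*

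**What the plan says.** Section 2.0, Objective 1, which is the primary objective, hypothesises "high intervention acceptability ratings from patients and key stakeholders". Among the means of testing it, the section lists "quantitative measures of patient satisfaction with the intervention (using the Client Satisfaction Questionnaire", the only quantitative patient satisfaction measure it names. No numeric threshold for acceptability is given.

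In Section 6.0 the questionnaire appears in the Time 3 list: "the Roland-Morris Pain and Pain-related Disability scale, the Client Satisfaction Questionnaire (8-item". That visit takes place "approximately 3 months after completing the intervention program, in order to assess long-term maintenance". Of Time 2, the same section says: "Participants will complete this assessment in the final weeks of the program". Its list of instruments contains no satisfaction scale.

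The population in Section 9.0 is older adults "with possible or pre-mild cognitive impairment (MCI".

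For retention and attendance, Objective 1 states: "The study protocol (MI-CBT KNA program) will result in high patient retention (90%) and patient attendance of intervention sessions (80" (the second figure is 80%). The targets are stated for the KNA programme; none is stated for the KN-only arm, and the time point at which retention is judged is not given.

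On the number of KNA meetings, Section 1.0 gives 6 and Section 5.0 gives 7 across 6 weeks.

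**The concern.** The pilot exists to judge feasibility and acceptability before a full-scale trial, so how patients rate the programme is central to it. A single rating taken at Time 3 has three weaknesses.

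- **Recall.** Every respondent rates a 6-week programme well after it ended, in a population chosen for possible early cognitive impairment.
- **Mixed target.** Time 3 is built around maintenance, and its interview asks about keeping to the diet in the long term. A rating given there may reflect the months since the programme as well as the programme itself.
- **Selection.** Those who leave the study or stop replying before Time 3 give no rating, and no rating at exit is described.

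A rating near the end of the programme cannot be recovered later if it was not taken. The protocol itself fixes both the instrument and its timing, so this is not a detail left to an analysis plan.

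**Working it through.** **1. Where satisfaction is scored.** Going through each assessment in Sections 5.0 and 6.0:

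- Screening call and Time 0 (health records): no satisfaction scale.
- Time 1 (baseline): none, as expected.
- Weekly surveys: none. They do cover barriers and facilitators to adherence, and group cohesion.
- Time 2: none. There is an interview on barriers and facilitators to completing the programme and keeping to the diet, a group cohesion scale and a global impression of change. None of these is a satisfaction rating.
- Time 3: Client Satisfaction Questionnaire, 8 items.
- Time 4: provider interviews and a provider fit scale; no patient satisfaction scale.

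The count is one scheduled administration, at Time 3.

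**2. Length of recall.** 3 months × (52 weeks / 12 months) = 13 weeks from programme end. At Time 2 the programme is still in its final weeks, or has just ended.

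**3. Participants not rated.** Inputs: 30 participants in the KNA arm (Section 12.0) and 90% retention (Section 2.0), assumed to hold to Time 3.

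- Unrated = 30 × (1 − 0.90) = 3, so 27 of 30 are rated.
- If retention were 80% or 70% (assumed values), unrated = 30 × 0.20 = 6 or 30 × 0.30 = 9.

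For a mean score, the mean over all 30 is 0.9 × (mean of the rated) + 0.1 × (mean of the unrated). The rated-only mean therefore differs from it by 0.1 × (rated mean − unrated mean). For any proportion, the value over all 30 is known only to within 3/30 = 10 percentage points, or 20 and 30 points at the two assumed lower retentions. The protocol sets no satisfied/not satisfied cut-off, so these widths describe missing information and are not tied to a decision rule.

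**4. Direction.** If dissatisfied people leave more often, the gap in step 3 is positive and the observed score is too high. If those who stay find the diet hard to keep up after the programme, their ratings may fall and the score is too low as a measure of the programme. The document gives nothing with which to weigh one against the other.

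**5. What a Time 2 form recovers.** It shortens recall for everyone who completes it. Of the 3 unrated in step 3, it recovers those who leave between Time 2 and Time 3, which is anywhere from 0 to 3.

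**6. Number of KNA meetings.** The week-by-week text in Section 5.0 appears to give 1 + 3 + 2 = 6. However, the Week 1 text also refers to the first meetings in the plural, and seven weekly meetings can span exactly six weeks if one is held at each end. The text does not settle the count. For the 80% attendance hypothesis, the protocol does not say whether it is scored per participant or for the group:

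- Per participant: attending 5 gives 5/6 = 83.3%, which meets 80%, but 5/7 = 71.4%, which does not.
- For the group: with average attendance p over six sessions and q at a seventh, the change is (6p + q)/7 − p = (q − p)/7. This is 0 if q = p, and 20/7 = 2.9 points if they differ by 20 points (assumed).

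**The case against.** The strongest reply is that nothing here is contradictory. Section 2.0 names the questionnaire without saying when it is given, and Section 6.0 then schedules it. Time 3 also has a rationale: the programme aims at long-term adherence and its last sessions deal with maintenance, so a later judgement is informative. Time 2 may fall before the last session. Acceptability is assessed by mixed methods, with interviews, weekly items, attendance and attrition all closer to the programme. Losses before Time 3 are limited because its questionnaires can be answered remotely, the visit is paid, and Section 13.0 allows up to three contact attempts and keeps participants who miss sessions but wish to stay.

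Most of this stands. It makes the point one of improvement, and it is why Time 3 should be kept. It does not supply the missing piece: interviews and cohesion items are not the satisfaction score that Objective 1 names, and remote completion neither shortens recall nor reaches people who have left.

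Three stronger readings are tempting, and the document does not support them:

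- A reader might infer that the Time 3 score will be too high. Step 4 of the working shows why the direction is unknown.
- A reader might infer that Section 4.0 drops patient satisfaction, because its quantitative measures run to "perception of the overall fit of the intervention in the clinic, and of patient intervention attendance and study attrition" without it. That section summarises and excludes nothing; staff following Section 6.0 would still collect the form.
- A reader might infer that 7 meetings is a slip for 6. The Week 1 wording and the calendar leave both possible, so a simple change to 6 could delete a real session.

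**Conclusion.** The point holds as a cheap improvement to a measure of the primary objective. As planned, the only quantitative patient satisfaction score rests on about 13 weeks of recall in people with possible or pre-MCI, may blend the programme with later experience of the diet, and omits those lost before Time 3. That loss is 3 of 30 KNA participants, assuming full enrolment with 30 in the arm and the 90% retention lasting to Time 3. It would be 6 or 9 of 30 at assumed retentions of 80% or 70%. How many would be lost from the KN-only arm cannot be derived from a stated target.

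The direction and size of any bias in the score are unknown, and no threshold exists against which a changed decision could be shown. The remaining evidence on acceptability and feasibility is not affected.

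The session count is a minor wording matter. It affects the result only if attendance is scored per participant, or if a seventh session is attended differently from the others.

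**What to change.** In Section 6.0, add the 8-item Client Satisfaction Questionnaire to the existing Time 2 assessment, completed at or after the last session where possible, for example through the REDCap link already used for remote questionnaires. In Section 13.0, offer it at withdrawal where the participant can be reached. Keep it at Time 3 as follow-up. Report the number rated out of the number randomised in each arm at each time point.

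The cost is a few minutes per participant and one added form. Two limits remain: Time 2 may still precede the last session for some, and some early leavers will still be missed.

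As a wording correction, confirm whether 6 or 7 KNA meetings are intended, make Sections 1.0 and 5.0 agree (describing the seventh meeting if there is one), and score the 80% attendance hypothesis on that count.

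### Section 6.0 gives the 3-month visit a phone and REDCap route but gives none for Time 2, so end-of-program FSQ, Roland-Morris and exit-interview data may be missed needlessly; other sections contradict the in-person mode

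*Protocol*

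**What the plan says.** All of this is in the Protocol.

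- **Time 2 (section 6.0, Post-intervention Assessment, Time 2).** The visit falls in the last weeks of the program so that participants are measured while in ketosis. On mode it says: "This assessment will be completed in-person following COVID-19 precautions, and patient participants will be compensated". No alternative is given. The content includes an interview on what helped or hindered adherence, the RBANS, the FSQ and, further down the list, "the Roland-Morris Pain and Pain-related Disability scale, the WHY-MPI, and participants' global impression of change, a second fasting blood draw". Body composition and vitals are also taken.
- **Time 3 (section 6.0, Post-intervention Assessment, Time 3).** About 3 months after the program: "Participants will complete the RBANS Update – form C, the PHQ-9, FSQ, MSQ, GAS, CAIDE Risk score", with the Roland-Morris later in the same list. The visit is in person by default, but "Participants who express barriers to completing the 3-month post-intervention assessment in person will have the option to complete this assessment remotely". On the remote route the interview is by phone and "participants will be asked to complete questionnaires via REDCap by following a link to the survey". One instrument is expressly dropped: "participants who choose to complete the Time 3 assessment remotely will not be asked to complete the RBANS".
- **Objective 2 (section 2.0).** The hypothesised effects include "improvements in daily functioning (FSQ), decreases in patient CAIDE risk score", and self-reported pain on the Roland-Morris.
- **Weekly survey (section 6.0, Weekly Assessments).** During the program, "participants will also complete a weekly online survey to assess information about their weight, health symptoms (MSQ), mood (PHQ-9"). The list goes on to anxiety, stress, ketones, adherence, pain, cohesion and support. It names neither the FSQ nor the Roland-Morris.
- **Statements of mode elsewhere.** The table in section 8.0 labels Time 2 a phone assessment. Section 23.0 puts all assessments on the telephone or Zoom. Section 24.0 calls them all virtual.

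**The concern.** The protocol foresees that some participants will have difficulty attending in person and writes a workable answer, but only for the later visit. The earlier visit is the one timed to the end of the intervention, so it is the natural point for comparing the two programs on function and pain. The questionnaires and the interview can be done at home. Losing them because the blood draw cannot be done would be avoidable.

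Missed Time 2 visits are foreseeable from the text. Section 14.0 tells people who feel sick to stay home, Time 2 sits in a narrow window with a morning fasting draw, and the program itself is delivered by Zoom. Difficulty in travelling could also be related to function and pain, which the FSQ and Roland-Morris measure, so the missing values might not be a random subset. That link is plausible, but the protocol gives no data on it.

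The contradictory statements of mode add to the problem. Staff reading sections 8.0, 23.0 or 24.0 could treat Time 2 as remote, and staff reading section 6.0 could not.

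**Working it through.** The protocol states no figure for Time 2 attendance, so there is nothing to reproduce. The check is mainly a comparison of the text, followed by an illustration of size.

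**1. Visits side by side (section 6.0)**

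| | Time 1 | Time 2 | Time 3 |
|---|---|---|---|
| Default mode | in person | in person | in person |
| Written remote route | none | none | phone plus REDCap |
| FSQ and Roland-Morris | yes | yes | yes |
| Participant interview | not listed | yes | yes, by phone if remote |
| Blood draw and body composition | yes | yes | not listed |
| Expressly dropped if remote | – | – | RBANS |

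That the FSQ and Roland-Morris can be given by REDCap is an inference. The Time 3 text speaks of questionnaires in general and names the RBANS as the one omission. Section 6.0 also already gives two FSQ sections by telephone at screening.

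**2. Can another source supply the Time 2 value?**

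- Time 3 repeats both scales, but about 3 months after the program, to study maintenance.
- The weekly survey has a pain measure but not the Roland-Morris, and no FSQ.
- The Time 4 record extraction may hold FSQ scores or notes on daily living, about six months after the program, where they were recorded.

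None of these is the end-of-program value.

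**3. Who would benefit?** Time 1 is in person too. Someone who never attends in person has no baseline Roland-Morris or full FSQ, so a remote Time 2 would give no complete change score. The gain is confined to participants who attended baseline, remain in the study and then cannot attend Time 2.

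**4. Conflict on mode.** Blood cannot be drawn, nor body composition measured as section 6.0 describes, by telephone or Zoom. Sections 8.0, 23.0 and 24.0 therefore cannot all be literally true alongside section 6.0. None of them describes a remote procedure for Time 2. The section 8.0 table also uses different visit labels: its T3 is a record extraction, whereas Time 3 in section 6.0 is the 3-month assessment.

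**5. Illustration of size.** Assume a proportion p of participants misses Time 2 (an assumption). Number missing = p × n. If missingness is unrelated to outcome, intervals widen by 1/√(1 − p).

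| p | of 60 (maximum) | of 40 (minimum) | of the 20 in the pain subsample | widening |
|---|---|---|---|---|
| 5% | 3 | 2 | 1 | 1/√0.95 = 1.026 |
| 10% | 6 | 4 | 2 | 1/√0.90 = 1.054 |
| 20% | 12 | 8 | 4 | 1/√0.80 = 1.118 |

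If non-attenders improve by d less than attenders, the available-case mean in an arm is too favourable by p × d, and the arm difference is biased by (p₁ − p₂) × d. With d = 0.5 SD and 5% missing in one arm against 15% to 20% in the other (all assumptions), the bias is 0.10 × 0.5 = 0.05 SD to 0.15 × 0.5 = 0.075 SD. With equal non-attendance it is zero. For comparison, the standard error of an arm difference at 30 per arm is √(2/30) = 0.26 SD, so even the larger bias is 0.075/0.26 = 0.29 of it.

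**The case against.** The strongest reply is that Time 2 is in person for good reason. It carries the RBANS, fasting bloods, vitals and body composition. These yield Objective 2 outcomes (HbA1c, the metabolic panel) and inputs to the CAIDE score, whereas Time 3 lists no blood draw. A freely available remote option would invite people to skip those measures. This stands against an open choice of mode. It does not stand against a last-resort route, because someone who would otherwise miss the visit gives no blood or RBANS in either case.

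Other points on that side do stand, and they rule out stronger readings:

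- A reader might infer that a missed Time 2 visit means no data at all. No passage says that questionnaires or the interview would be withheld. Time 2 already lets ketone logs come back electronically, by phone or by mail, and section 16.0 describes data collection by REDCap or telephone. The gap is the absence of a written route, not a prohibition.
- A reader might infer that the post-program FSQ and Roland-Morris are lost altogether. They are repeated at Time 3 with a remote option; only the end-of-program value is at risk.
- A reader might infer that the protocol as a whole confines remote assessment to Time 3. Sections 8.0, 23.0 and 24.0 say otherwise. The gap is within section 6.0, and the document contradicts itself.
- A reader might infer damage to the 90% retention result. Section 13.0 defines premature discontinuation by withdrawal, or by non-response after repeated unannounced absences, and does not remove people for missing assessments. One missed visit is not attrition under that rule, although the same section defines completion as including the assessments. Failure to attend is also feasibility information in its own right.
- A reader might use the 90% target to size the loss. It covers all causes, and people who leave the study are not recovered by a survey link.

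**Conclusion.** The point holds in a limited form. Section 6.0 writes a remote procedure for one post-program visit and not for the other, so a participant who attended baseline but cannot attend Time 2 has no stated way to give the end-of-program FSQ, Roland-Morris and exit interview. Separately, sections 8.0, 23.0 and 24.0 conflict with section 6.0 on how assessments are done.

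The likely effect is modest and its size is unknown. The illustrative 3 to 12 of 60 rests on an assumed 5% to 20% non-attendance, and not all of those people could be recovered. A serious bias in the arm comparison is not supported: the figures above need an assumed imbalance between randomised arms for which the protocol offers no mechanism, and they remain well below the standard error. Section 2.0 also limits the comparison to visual examination without significance testing. This is a low-cost improvement to data completeness and a needed clarification of mode, not a flaw that undermines the trial.

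**What to change.** 1. In section 6.0, Time 2, allow the remote procedure already written for Time 3 (phone interview, questionnaires by REDCap link) only when the in-person visit would otherwise be missed.
2. For such visits, record the RBANS, bloods, vitals and body composition as not done.
3. Record the mode of each Time 2 assessment and report it by arm, with the number in each arm who missed the visit altogether.
4. Reconcile sections 8.0, 23.0 and 24.0 with section 6.0, so that the protocol says once which assessments are in person and which may be remote.

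**Cost.** Protocol wording, plus a small change to the survey set already provided for at Time 3, because the two questionnaire lists differ slightly (for example, group cohesion is listed only at Time 2 and the satisfaction questionnaire only at Time 3). The downside is that a few participants might choose the remote route and forgo the RBANS and blood draw. Offering it only as a last resort limits this, and reporting mode by arm would show it.
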